### Number of Participants:

Approximately 100 total participants may be allocated/randomized in Part 1 (n=28, actual sample size as Part 1 is clinically complete) and Part 2 (n ~72). In Part 1, approximately 16 evaluable participants with schizophrenia will complete a generally well-tolerated dose titration.

In Part 2, the intent is to evaluate up to 2 panels of elderly participants with schizophrenia (Panel D and Panel E) and up to 2 panels of healthy elderly participants (Panel F and Panel G).

Up to approximately 16 participants may be enrolled in Panel D and up to approximately 24 participants may be enrolled in Panel E to ensure approximately 16 elderly participants with schizophrenia complete a generally well-tolerated dose titration. Up to approximately 12 participants will be enrolled in Panel F and up to approximately 20 participants will be enrolled in Panel G to ensure approximately 12 healthy elderly participants complete a generally well-tolerated dose titration as described in Section 9.9.

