In P005, for the primary endpoint of PANSS total score change from baseline at Week 4, although the MK-8189 group showed meaningful improvement in symptoms, the improvement missed statistical significance (difference [95% CI] in LS mean change was -4.7 [-9.8, 0.5];  $p=0.074$ ). Risperidone was superior to placebo with respect to this endpoint (difference [95% CI] in LS mean change was -7.3 [-14.0, -0.6];  $p=0.033$ ). There was no difference in magnitude of effect between MK-8189 and risperidone (difference [95% CI] in LS mean change was 2.6 [-4.0, 9.2];  $p=0.440$ ). For the exploratory endpoint of PANSS positive subscale score at Week 4, both MK-8189 and risperidone were superior to placebo. There was no significant difference in effect between MK-8189 and risperidone. Neither risperidone nor MK-8189 demonstrated significant improvement in the CGI-S.

Median Tmax of MK-8189 as monotherapy ranged from 10 to 20 hours with a t1/2 of approximately 8.4 hours (37.8% GCV).

Data suggest that the exposures at steady state for a given dose are generally lower in healthy participants compared to participants with schizophrenia administered MK-8189 as monotherapy.

In a DDI study (P006) the coadministration of extended release 240-mg diltiazem increased MK-8189 AUC and Cmax by approximately 2-fold and 1.3-fold, respectively, confirming that MK-8189 is a CYP3A substrate.

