## 3 HYPOTHESES, OBJECTIVES, AND ENDPOINTS

There are no hypotheses for this study.

In male or female participants with schizophrenia (young adults and elderly) and healthy elderly participants:

Objectives	Endpoints
Primary	
Part 1 

To evaluate the safety and tolerability of MK-8189 oral, once-daily titration regimens in young adult participants with schizophrenia

	Part 1 and Part 2 

Adverse experiences, laboratory safety tests, electrocardiograms and vital signs

Part 2 

To evaluate the safety and tolerability of multiple once-daily oral doses of MK-8189 in elderly participants with schizophrenia and healthy elderly participants

	

Objectives	Endpoints
Secondary	
Part 1 

To characterize MK-8189 pharmacokinetics following different titration regimens in young adult participants with schizophrenia

	Part 1 and Part 2 

AUC0-24hr, Cmax, C24hr, Tmax, CL, Vd and apparent t1/2

Part 2 

To characterize the pharmacokinetics of MK-8189 following multiple once-daily oral doses in elderly participants with schizophrenia and healthy elderly participants.

	
Tertiary/Exploratory	
Part 1 and Part 2 

To investigate the relationship between CYP2C9 genetic polymorphisms and the PK of MK-8189. Genetic variation in CYP2C9 may be analyzed for association with any laboratory or clinical data collected in this study.

To explore the relationship between genetic variation and response to the treatment administered, and mechanisms of disease. Variation across the human genome may be analyzed for association with clinical data collected in this study.

	Part 1 and Part 2 

Germline genetic variation in CYP2C9 and association to clinical data collected in this study

Germline genetic variation and association to clinical data collected in this study.

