## 6.3 Measures to Minimize Bias: Randomization and Blinding

### 6.3.1 Intervention Assignment

Participants will be assigned randomly according to a computer-generated allocation schedule.

The sample allocation schedule for Parts 1 and 2 is provided in [Table 2].

Table 2 Sample Allocation Schedule

Part 1							
Panel	Patients (n)	Day 1	Day 2	Day 3	Days 4-7		
A	12	16 mg QD			24 mg QD		
	4	PBO			PBO		
B	12	24 mg					
	4	PBO					
C	12	8 mg QD	16 mg QD	24 mg QD			
	4	PBO	PBO	PBO			
Part 2							
Panel	Patients (n)	Days 1-3	Days 4-6	Days 7-13			
D/F	12 (Panel D); 10 (Panel F)	8 mg QD	16 mg QD	24 mg QD			
	4 (Panel D); 2 (Panel F)	PBO	PBO	PBO			
Part 2							
Panel	Patients (n)	Days 1-3	Days 4-10				
E/G TR1	12 (Panel E); 10 (Panel G)	16 mg QD	24 mg QD				
	4 (Panel E); 2 (Panel G)	PBO	PBO				
Part 2							
Panel	Patients (n)	Days 1-7					
E/G TR 2	12 (Panel E); 10 (Panel G)	24 mg QD					
	4 (Panel E); 2 (Panel G)	PBO					
Part 2							
Panel	Patients (n)	Day 1	Day 2	Days 3-9			
E/G TR 3	12 (Panel E); 10 (Panel G)	8 mg QD	16 mg QD	24 mg QD			
	4 (Panel E) 2 (Panel G)	PBO	PBO	PBO			

TR = Titration Regimen; n=number; PBO=placebo; QD=once daily

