**Pharmacokinetics:**

Separately for each part and each PK parameter, individual values of AUC0-24hr, Cmax, and C24hr at each dose level will be natural log-transformed and evaluated with a linear mixed effects model containing a fixed effect for dose and a random effect for subject. For each PK parameter, GM and corresponding ninety-five percent Cis for each dose will be provided.

The comparison of elderly participants with schizophrenia to young adults with schizophrenia will be made using data from Part 2 and Part 1, and historical data from P007 (Panel B and D). Separately for each PK parameter individual values of AUC0-24hr, Cmax, and C24hr at each dose level (16 mg and 24 mg at steady state) will be natural log-transformed and evaluated with a linear mixed effects model containing fixed effects for dose, population (elderly, adult), and population by dose interaction and a random effect for subject. For each population, GMs and corresponding 95% CIs for each dose will be provided. Similarly, the comparison of healthy elderly participants (Panels F and G) to healthy young adults (Panel A in P007) will be made using the above described model.

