## Pharmacokinetics

Separately for each part and each PK parameter, individual values of AUC0-24hr, Cmax, and C24hr at each dose level will be natural log-transformed and evaluated with a linear mixed effects model containing a fixed effect for dose and a random effect for subject. For each PK parameter, GM and corresponding 95% CI for each dose will be provided.

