## 9.9 Sample Size and Power Calculations

Since there are no hypotheses, no power calculations are provided.

Comparison of Elderly vs Young Adults (Exploratory): The between-subject standard deviation estimates for healthy and participants with schizophrenia used in the calculations below were obtained from 24 mg dose in MK-8189 PN007 Panel A and Panel B, respectively. At each of the comparable doses, the precision of the estimates of GMR obtained from the study can be assessed by calculating the half-width of the 90% CIs for the GMRs (elderly/adults) expected for the given sample size and assumed between-subject standard deviation. [Table 4] below shows the half-width of the 90% CI for the true GMR for PK parameters, AUC0-24hr, Cmax, and C24hr.

Table 4 Precision Estimates for AUC0-24hr, Cmax, and C24hr

PK Parameter	Observed (Log) Between-Subject SD	N	(Log) Half-Width of 90% CI	Observed GMR (elderly/adults)	90% CI Based on Observed GMR
elderly with schizophrenia vs adults with schizophrenia					
AUC0-24hr	0.38	12 elderly 12 adults	0.266	1.00	(0.77, 1.31)
Cmax	0.37	12 elderly 12 adults	0.259	1.00	(0.77, 1.30)
C24hr	0.48	12 elderly 12 adults	0.336	1.00	(0.71, 1.40)
healthy elderly vs healthy adults					
AUC0-24hr	0.60	10 elderly 12 adults	0.443	1.00	(0.64, 1.56)
Cmax	0.48	10 elderly 12 adults	0.354	1.00	(0.70, 1.43)
C24hr	1.11	10 elderly 12 adults	0.822	1.00	(0.44, 2.27)
AUC=area under the time-concentration curve from 0 to 24 hours; C24hr=concentration at 24 hours; CI=confidence interval; Cmax=maximum concentration; GMR=geometric mean ratio; N=number; PK = pharmacokinetic, SD = standard deviation ,					

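### Minor: the by-part PK model pools schizophrenia with healthy elderly participants in Part 2 and does not say which profile day its 24-mg mean describes

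*Combined protocol and SAP*

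**What the plan says.** Section 9.6, Pharmacokinetics, takes "Separately for each part and each PK parameter, individual values of AUC0-24hr, Cmax, and C24hr at each dose level", log-transforms them, and has them "evaluated with a linear mixed effects model containing a fixed effect for dose and a random effect for subject". Section 9.1 describes the same model and states its output: "GM and corresponding ninety-five percent Cis for each dose will be provided". Neither section has a term or restriction for population, panel, regimen or day.

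Part 2 contains two populations (Section 4.1): elderly participants with schizophrenia in Panels D and E, and healthy elderly participants in Panels F and G. The Part 2 secondary objective in Section 3 is to characterize PK "following multiple once-daily oral doses in elderly participants with schizophrenia and healthy elderly participants". Section 2.2.2 says that data suggest "exposures at steady state for a given dose are generally lower in healthy participants compared to participants with schizophrenia" given monotherapy. Section 9.9 treats the populations separately: "The between-subject standard deviation estimates for healthy and participants with schizophrenia used in the calculations below were obtained from 24 mg dose" in two different P007 panels.

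Two neighbouring paragraphs of Section 9.6 are more specific. The comparison of elderly participants with young adults covers 16 and 24 mg at steady state. It is run once for schizophrenia and once for healthy participants, and gives GMs with 95% CIs per population and dose. The descriptive statistics go by part, panel, dose and, where applicable, day.

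**The concern.** The by-part model is the only model-based estimate tied to the secondary PK objective. In Part 2 its GM per dose is an average over two populations that the documents themselves expect to differ in level and in spread. One subject variance is applied to both.

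The 24-mg GM has a second gap. Every regimen schedules a full 24-mg profile on the first 24-mg day and another on the last. Read literally, both enter as replicates of one 24-mg mean. If only one is meant, it is not named.

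The stake is a clear report. A 24-mg GM and CI could appear that match neither the population-specific nor the day-specific GMs printed beside them. Regimens are chosen on safety and tolerability, so no design decision is at risk.

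**Working it through.** **1. Table 4 reproduced.** Half-width = t(0.95, n1+n2−2) × SD × √(1/n1 + 1/n2).
- Schizophrenia AUC: 1.717 × 0.38 × √(1/12 + 1/12) = 0.266 (stated 0.266).
- Healthy AUC: 1.725 × 0.60 × √(1/10 + 1/12) = 0.443 (stated 0.443).
- Healthy C24hr, with SD 1.11: 0.820 (stated 0.822, consistent with rounding of the SD).

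The SDs can therefore be used as between-subject log SDs.

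**2. Variance ratios, healthy to schizophrenia.**
- AUC: (0.60/0.38)² = 2.5
- Cmax: (0.48/0.37)² = 1.7
- C24hr: (1.11/0.48)² = 5.3

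A common C24hr SD with 24 and 20 active participants (Table 2: 12 + 12 and 10 + 10) would be √[(24 × 0.48² + 20 × 1.11²)/44] = 0.83. That is 1.7 times the schizophrenia SD and 0.75 times the healthy SD.

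**3. Mixing of means (illustration).** The documents give no exposure ratio r (healthy/schizophrenia). With equal weight per participant, pooled GM/schizophrenia GM = r^(20/44) and pooled GM/healthy GM = r^(−24/44).

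| Assumed r | Pooled vs schizophrenia | Pooled vs healthy |
|---|---|---|
| 0.9 | 0.95 | 1.06 |
| 0.8 | 0.90 | 1.13 |
| 0.7 | 0.85 | 1.22 |

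**4. Profile days.** From the dosing tables and the PK footnotes in Sections 1.3.1 to 1.3.5. Where no 24-hour sample is listed, the next predose sample supplies it.

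| Panel/regimen | 24-mg days | Full 24-mg profiles | 16-mg days | Full 16-mg profile |
|---|---|---|---|---|
| A | 4–7 | 4, 7 | 1–3 | 1 |
| B | 1–7 | 1, 7 | none | none |
| C | 3–7 | 3, 7 | 2 | 2 |
| D/F | 7–13 | 7, 13 | 4–6 | 4 |
| E/G Regimen 1 | 4–10 | 4, 10 | 1–3 | 1 |
| E/G Regimen 2 | 1–7 | 1, 7 | none | none |
| E/G Regimen 3 | 3–9 | 3, 9 | 2 | 2 |

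The last column also touches the age comparison. AUC and Cmax at 16 mg can come only from the first 16-mg day, which in Regimen 1 is the first dose ever given. The steady-state label does not fit them. C24hr differs: the Day 7 predose sample in D/F and the Day 4 predose sample in Regimen 1 follow the third 16-mg dose.

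**5. Size of the day effect on AUC if both days enter (illustration).** Assume linear one-compartment PK with a half-life of 8.4 h (Section 2.2.2). The fraction left after 24 h is 0.5^(24/8.4) = 0.138.
- With instantaneous absorption, first-day/last-day AUC is 1 − 0.138 = 0.862 for Regimen 2 and 1 − (8/24) × 0.138 = 0.954 for D/F, taking 16 mg as at steady state. The two-day GM is the square root of the ratio: 0.93 and 0.98 of the last-day GM.
- With first-order absorption and Tmax 10 to 12 h, the ratios are 0.68 to 0.59 (Regimen 2) and 0.89 to 0.86 (D/F). The two-day GM is then 0.82 to 0.77 and 0.94 to 0.93 of the last-day GM.

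**6. Price of splitting.** 95% CI factor = exp(t × SD/√n), for AUC on the last day with all panels full.
- Schizophrenia, n = 24: exp(2.069 × 0.38/√24) = 1.17
- Healthy, n = 20: exp(2.093 × 0.60/√20) = 1.32
- Pooled, n = 44, SD 0.492: exp(2.017 × 0.492/√44) = 1.16

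**The case against.** The strongest reply is that the useful estimate is already planned. The age comparison gives steady-state 24-mg GMs with 95% CIs separately for elderly participants with schizophrenia and healthy elderly participants, and the descriptive tables give GMs by panel, dose and day. This stands, and it confines the point to the model-based secondary summary. What remains uncovered is 8 mg in Part 2, which the age comparison omits, and Part 1 alone, which that comparison combines with P007 data. At 8 mg the mixing of means may be small, since Section 4.2 places the possible population difference above 12 mg.

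A second reply is that a dose effect with a random subject effect ordinarily means one value per participant per dose. That reading is possible. Nothing would then be mixed across days, and the defect shrinks to an unnamed day.

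A reader might go further and infer that the reported 24-mg GM will be low by a definite percentage. The documents do not support that. It needs the literal two-day reading and an assumed absorption model, and Section 2.2.2 gives a median Tmax range of 10 to 20 h and a half-life with 37.8% GCV. A reader might also infer that every active participant contributes both 24-mg profiles. Sections 4.1 and 6.6 allow holding, down-titration and stopping, and Section 8.6 lets the sponsor choose which samples are assayed.

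**Conclusion.** The point holds as a minor one. The population part is the firmer: followed as written, the Part 2 model gives one GM and CI for a mixture of two populations with unequal assumed variances (ratios of about 2.5 for AUC and 5.3 for C24hr, from Table 4). The shift in the mean cannot be sized from the documents; step 3 only shows what assumed ratios would do.

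The day part is real but weaker. Two 24-mg profile days exist in every regimen and the by-part text omits the steady-state restriction used in the age comparison, but a one-value reading is open. The percentages in step 5 are illustrations under assumed PK and should not be cited as bias in this trial.

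It would be tempting to treat the age comparison as wholly clear of the day problem because it specifies steady state. That is right at 24 mg, but at 16 mg the label is unsupported for AUC and Cmax. The opposite inference, that the age comparison is invalid, does not follow either: its population split is correct and its 24-mg estimate is well defined.

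**What to change.** In Sections 9.1 and 9.6:
- Fit the Part 2 by-part model separately for schizophrenia (Panels D/E) and healthy elderly participants (Panels F/G).
- In both parts, restrict the 24-mg estimate to the last 24-mg day (Day 7 in Part 1; Day 13 in D/F; Day 10, 7 or 9 in E/G Regimens 1, 2 and 3). Leave first-day values to the by-day descriptive tables.
- In the age comparison, label 16-mg AUC0-24hr and Cmax by the day actually profiled instead of as steady state.

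A dose-by-day-by-regimen model is not needed to repair the defect.

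The cost is wording only, with no new data or procedures. Section 9.2 already provides for listing such changes in the study report. The AUC interval is almost unchanged for schizophrenia (×/÷1.17 against ×/÷1.16 pooled) and wider for healthy elderly participants (×/÷1.32). The latter reflects that group's larger assumed variability, which pooling would understate. These widths assume that all four panels fill; with one panel per population they are about ×/÷1.27 (n = 12) and ×/÷1.54 (n = 10).

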### Comparison of Elderly Participants and Young Adults

The comparison of elderly participants with schizophrenia to young adults with schizophrenia will be made using data from Part 2 (Panels D and E) and Part 1, and historical data from P007 (Panels B and D). Separately for each PK parameter, individual values of AUC0-24hr, Cmax, and C24hr at each dose level (16 mg and 24 mg at steady state) will be natural log-transformed and evaluated with a linear mixed effects model containing fixed effects for dose, population (elderly, adult), and population by dose interaction and a random effect for subject. Kenward and Roger's method will be used to calculate the denominator degrees of freedom for the fixed effects. For each population, 95% CIs for the least squares means for each dose will be constructed on the natural log scale. Exponentiating the least-squares means, and lower and upper limits of these CIs will yield estimates for the population GMs and CIs about the GMs on the original scale. Individual PK values, GMs and 95% CIs will be shown graphically by population. A two-sided 90% CIs for the true differences in mean for log-transformed AUC0-24hr, Cmax, and C24hr (elderly – adults) will also be computed from the model. These CIs will be exponentiated to obtain the 90% CIs for the AUC0-24hr, Cmax, and C24hr true geometric mean ratios (elderly/adults). Additionally, a plot of GMR with corresponding 90% CI will also be provided.

Similarly, the comparison of healthy elderly participants (Panels F and G) to healthy young adults (Panel A in P007) will be made using the above described model.

The exploratory objective pertaining to the assessment of relationship between CYP2C9 genetic polymorphs and the laboratory, and PK of MK-8189, and the relationship between genetic variation and response to the treatment may be addressed in a separate report.

